Percutaneous radiofrequency ablation (RFA) of peripheral cancers is the most studied of the ablative modalities which has been used in medically inoperable patients with small (< 3 cm) peripheral stage I NSCLC (Howington *et al.*, 2013). Although, there is currently no comparative studies, the local control rates seem lower than those reported with SABR or sublobar resection (Howington *et al.*, 2013; Donington *et al.*, 2012). Tumors larger than 3 cm had the highest local recurrence rate (50%) and thus ideal lesions for this treatment should include lesions less than 3 cm in size (Lanuti *et al.*, 2009). Studies show a consistent local control rate of 60%, with a 30% to 40% overall survival at 3 years and a cancer-specific survival of 30% to 40% at 5 years. These

outcomes are better than those seen in untreated patients with clinical stage I NSCLC but worse than those reported with SABR or sublobar resection. In the studies specifically addressing the inoperable stage I NSCLC, the primary tumor relapse rate after percutaneous RFA ranges from 8% to 43% (Donington *et al.*, 2012). The most common reported complications were pneumothorax (18%-62%), pleural effusion (7%-21%), and hemoptysis (4%-11%). Chest tube drainage was required in 5%-25% of subjects. There are also reports of bronchopleural fistula and massive hemoptysis.

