***Surgery and post-surgery care***

1. Surgery and post-surgery care as per standard of care.
2. Reduced light settings and subject draping will be used to avoid potential problems from bright surgical lights:
  - from the moment the subject enters the hospital and will continue while the subject is in the surgical suite and on the surgical care units;

- surgery will be performed with room lights which are modified by amber filters that block wavelength below 550 nm;
- incisions will be shielded from inadvertent light exposure (e.g., sterile blue towels);
- remainder of the subject's skin will be draped in the usual surgical manner.

In addition, measuring oxygen saturation with pulse oximetry (pulse ox) will expose the skin to red light, which may cause skin burns if left in one place too long. Continuous monitoring can be carried out by setting up multiple monitors and rotating on and off status of the fixed sensors, or by moving a single sensor to different pulsating arteriolar bed, such as the finger, great toe, nose, or earlobe.

3. Record concomitant medications and adverse events.
4. Macroscopic and microscopic examinations of lung tumor tissue and lung healthy tissue. Lung tissue following surgical resection will be sent to the local pathology lab for macroscopic examination. Slides for microscopic examination will be prepared by the local pathology lab and sent to an independent expert pathologist (ARUP Laboratories, Salt Lake City, UT, USA) for central reading. The central assessor will interpret all histology samples obtained through surgery across all sites. Procedures for slide preparation and shipment will be performed as per laboratory instructions provided to participating sites.
5. Re-educate the subject on how to manage light exposure.

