3. DATA ANALYSIS CONSIDERATIONS

3.1 Determination of Sample Size

This study is designed to assess the safety of PDT in subjects with solid lung tumors prior to surgical resection and to assess the lung tumor and healthy tissue response to PDT. The intent of this study is to enroll 10 subjects. This sample size has the following precision for estimation of rates of AE's of special interest (AESI). The following table shows historical AE rates for RFA ranging from <1 to $\sim50\%$.

AESI	Rate Observed with RFA				
Pneumothorax	11-52%				
Pleural effusion	6-19%				
Hemorrhage	6-18%				
Pulmonary artery pseudoaneurysm	0.2%				
Needle tract seeding	0.3-0.7%				
Cavitation	14%				
Bronchopleural fistula	0.6%				
Pneumonitis	0.4%				

The sample size of N=10 has precision for estimation of AE rates for estimates ranging from <0.01 to ~0.5 as shown in the following list. Precision is measured by 1-sided 95% upper confidence limit (CL) on the estimated AE rate via exact binomial distribution. PDT is expected to have lower AE rates than RFA, so, for example, for a RFA historical rate of 0.27 (27%), if no such AE's are observed on PDT, then the TRUE underlying PDT rate is lower than 0.27 with 95% confidence since the upper 95% CL is 0.26 - indicated by "*" in the list below.

No. of AESIs	Rate	Upper 1-sided 95% confidence limit
0	0.00	0.26*
1	0.10	0.39
2	0.20	0.51
3	0.30	0.61
4	0.40	0.70
5	0.50	0.78

The study will be suspended and re-evaluated from a safety standpoint if 20% of the subjects experience a serious adverse event that is related to PDT.

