5.4.11.1 Adverse Events

Adverse Events will be coded using the Medical Dictionary of Regulatory Activities (MedDRA version 20.0) AE coding system for purpose of summarization.

Events collected at the "NCS Events" CRF page will be summarized together with Adverse Events, but excluded from analyses by CTCAE grade and relationship to study drug, since these data points are not captured for NCS events.

An AE will be defined as treatment-emergent (TEAE) if its date of onset is on or after the date of the study drug (PHO) administration.

An AE will be defined as treatment-related if its relationship to the study drug is recorded as "Reasonable Possibility" on the CRF.

An overall summary of number and percentage of subjects with at least one AE, TEAE, serious TEAE, treatment-related TEAE, serious treatment-related TEAE, TEAE leading to discontinuation and fatal TEAE will be presented.

A summary of the frequency (number and percentage of subjects) of TEAEs will be presented by system organ class and preferred term. One-sided 95% upper confidence limit will be computed for each AE percentage via exact (Clopper-Pearson) method for binomial proportion. Adverse events will also be analyzed by their CTCAE grade (1 to 5) and relationship to study drug (related or not related).

A subject experiencing the same AE multiple times will be counted only once for that preferred term. Similarly, if a subject experiences multiple AEs (preferred terms) within the same system organ class, then that subject will be counted only once for that system organ class. When summarizing by CTCAE grade and relationship, only event with highest grade or relationship will be counted. All AEs will be presented in alphabetical order of SOC and preferred terms.

Skin photosensitivity is an adverse event of special interest (AESI). Skin photosensitivity will be summarized separately by SOC and preferred term as well as by SOC, preferred term and CTCAE grade.

All information pertaining to adverse events noted during the study will be listed by subject, detailing verbatim term given by the investigator, preferred term, system organ class, start date, stop date, CTCAE grade, outcome, action taken and drug relatedness. Separate listings will be created for Serious TEAEs, TEAEs leading to study drug discontinuation and skin photosensitivity events.

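### SAP 3.1 justifies N=10 by upper limits on eight lung AESIs, but SAP 5.4.11.1 has no dedicated table for them and computes its limits over a window that includes lung resection; the comparison with RFA is affected only for pneumothorax

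*SAP*

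**What the plan says.** SAP 3.1 (same text in Protocol 10.1) presents the sample size as precision for AESI rates. It lists eight events with RFA rates: pneumothorax 11-52%, pleural effusion 6-19%, hemorrhage 6-18%, cavitation 14%, and four below 1% (pulmonary artery pseudoaneurysm, needle tract seeding, bronchopleural fistula, pneumonitis). It expects lower rates with PDT and gives an example for an RFA rate of 0.27: "if no such AE's are observed on PDT, then the TRUE underlying PDT rate is lower than 0.27 with 95% confidence".

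SAP 5.4.11.1 is the analysis section. The only AESI it names is skin photosensitivity, which is not among the eight. The main display is described thus: "A summary of the frequency (number and percentage of subjects) of TEAEs will be presented by system organ class and preferred term". Each AE percentage gets an exact one-sided 95% upper limit. An AE is treatment-emergent "if its date of onset is on or after the date of the study drug (PHO) administration"; there is no end date and no split at surgery. A further analysis is by relationship to study drug, and NCS events are left out of it.

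Surgery is on Day 13-18 and study exit on Day 103-108 (SAP 2.2.1). The protocol's list for surgery and post-surgery care includes "Record concomitant medications and adverse events". SAP section 6 declares no change from the protocol analyses.

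**The concern.** The sizing section says what the limits are for, and the analysis section does not produce them in that form. Pneumothorax, effusion and bleeding are events that a lung resection can cause by itself. Protocol 1.1.1 describes RFA as "the most studied of the ablative modalities which has been used in medically inoperable patients", so the historical rates presumably come from patients who were not resected soon afterwards. A planned row that counts post-resection events is then not like for like with the RFA figure.

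AE incidence is the primary endpoint, so the row will be read as the PDT rate. Counting all TEAEs can overstate that rate. Counting only drug-related events can understate it, if sites call a pneumothorax from fiber placement unrelated to the drug. The limit is planned on all TEAEs. A split by period would have to be made from listings, with window, denominator and terms chosen after the data are seen.

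**Working it through.** **1. The plan's own limits.** For x of n subjects the one-sided 95% Clopper-Pearson limit U solves P(X ≤ x | n, U) = 0.05. For x = 0, U = 1 − 0.05^(1/n). With n = 10 and x = 0 to 5 this gives 0.259, 0.394, 0.507, 0.607, 0.696 and 0.778. All six agree with SAP 3.1 after rounding.

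**2. Which RFA comparisons are possible at all.** The smallest limit at n = 10 is 0.259.
- Effusion (top RFA rate 19%), hemorrhage (18%), cavitation (14%) and the four events below 1%: all are under 0.259. No window and no result can put the limit below the RFA rate. Protocol 1.1.1 gives slightly different RFA figures (effusion up to 21%, hemoptysis up to 11%), which lead to the same conclusion.
- Pneumothorax (11-52%): 0/10 falls below RFA rates above 0.259. Against 52%, up to two affected subjects are allowed (0.507); a third gives 0.607. Against 11%, even 0/10 is not enough.

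**3. Share of the window after surgery.** Surgery on Day 13 with exit on Day 103: 90/103 = 87%. Surgery on Day 18 with exit on Day 108: 90/108 = 83%.

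**4. Effect on the pneumothorax row.** Let p be the chance of a pneumothorax from PDT and its bronchoscopy, and q the chance from resection, taken as independent. Over the whole study r = 1 − (1 − p)(1 − q), and the number affected is Bin(10, r). Inputs:
- p = 0.06, from the chart review of 98 navigation procedures in Protocol 1.2. These were diagnostic procedures, so this is a stand-in for fiber placement.
- q = 5-30%, an assumption; the documents give no rate.

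| q | r | P(0/10) = (1 − r)^10 | P(at most 2/10), limit below 0.52 | Mean limit |
|---|---|---|---|---|
| 0 (before surgery only) | 0.060 | 0.54 | 0.98 | 0.337 |
| 0.05 | 0.107 | 0.32 | 0.92 | 0.393 |
| 0.10 | 0.154 | 0.19 | 0.81 | 0.447 |
| 0.20 | 0.248 | 0.06 | 0.53 | 0.545 |
| 0.30 | 0.342 | 0.02 | 0.28 | 0.634 |

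Other values of p, for P(0/10): at p = 0.03, 0.74 falls to 0.44-0.02; at p = 0.10, 0.35 falls to 0.21-0.01. With p = 0, the mean limit rises from 0.259 to 0.324, 0.385, 0.496 and 0.596 at the four resection rates.

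**5. Denominator.** The Safety Population is everyone injected, with or without light treatment. If one of ten gets no PDT, the relevant limit for no events is that for 0/9: 1 − 0.05^(1/9) = 0.283. This is above the 0.27 of the example.

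**6. Ungrouped terms.** Suppose hemorrhage is coded to one of two preferred terms with equal chance. The largest row then understates affected subjects with probability 1 − [2(1 − h/2)^10 − (1 − h)^10]. This is 0.06 at h = 0.06 and 0.36 at h = 0.18, and it is zero if one term is always used. This is a smaller matter than the window.

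**The case against.** The trial is a descriptive Phase Ib study. The RFA comparison is offered as an example, with no hypothesis or decision rule, and 0.27 is not itself a listed RFA rate. The whole-study window matches the stated evaluation to 90 days after surgery (SAP 2.2) and errs against PDT. An AESI that occurs does get a row and an exact limit, and the limit for 0/10 is already printed in SAP 3.1. All of this stands. What is missing is a dedicated, grouped table. Nothing requires a row for an AESI with no events, which is the case the example uses.

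Some separation already exists. Protocol 8.4.2 asks investigators to consider devices and laser light as well as drug, and accepts other therapy, including non-drug therapy, as grounds for no reasonable possibility. The Day 5 chest X-ray is summarized, and the pre-surgery CT, surgery details and AE start dates are listed. With about ten subjects a split could be made by hand. This too stands in part. The SAP words the table as relationship to study drug, so how a fiber-placement event is classed depends on the CRF and the site. NCS events are excluded, and the sentence on limits follows the all-TEAE table. It would be too strong to infer that the relationship table must fail; the documents show only that it may not separate the two sources.

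A reader might also infer that mixing with resection is what defeats the RFA comparison for effusion and bleeding. The documents do not support that. At N=10 those comparisons are out of reach in any window.

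Finally, a pre-surgery window is short, and the follow-up behind the SAP 3.1 RFA rates is not given, nor is their population. A comparison limited to that window may favor PDT.

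**Conclusion.** The point holds in limited form. As written, any AESI row that resection can also feed gives a limit for PDT plus resection, and the other planned outputs separate the two only partly. The comparison with RFA can change only for pneumothorax, and only against the part of the RFA range above 0.26. For the other seven AESIs the obstacle is N=10.

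For pneumothorax the effect could be large. With 6% procedural risk, the chance of 0/10 falls from 54% to 32%, 19%, 6% or 2% at resection rates of 5%, 10%, 20% or 30%. Those rates are assumed, the two risks are treated as independent, and the 6% is borrowed from diagnostic bronchoscopy. If resection adds no recorded event the effect is nil. The suspension rule rests on related serious events and does not use these limits. The data needed are already collected, so this is a gap in prespecification and not in data collection.

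**What to change.** Add one table to SAP 5.4.11.1 with the eight AESIs of SAP 3.1 as rows, including rows with no events. Fix each row's MedDRA 20.0 preferred terms from the dictionary, not from the study's own AE listing, and date the list. Hemorrhage should include at least hemoptysis and airway or lung bleeding. Count each subject once per row and window, include NCS events, and give n, % and the exact one-sided 95% upper limit for:

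- **Window A:** onset from the start of PDT bronchoscopy to surgery (to Day 18 if there is no surgery), among subjects who received PDT.
- **Window B:** onset from surgery to study exit, among subjects who had surgery. Events on the day of surgery go here unless found at the pre-surgery assessment or CT.
- **Whole study:** the existing TEAE rows, kept alongside. They also hold events between injection and bronchoscopy, which fall in neither window.

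Use Window A for the pneumothorax comparison with RFA. State that N=10 cannot show a rate below RFA for the other seven AESIs.

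The cost is SAP wording, a term list and one table built from coded terms and onset dates already planned for listing. The drawback is that Window A covers only about 10-15 days after PDT. Later PDT events fall in Window B, so the Window A comparison may favor PDT. Both windows and the whole-study row must therefore be shown together, with that caution stated.

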5.4.11.2 Clinical Laboratory Parameters

Samples will be obtained for the clinical laboratory tests at the following time points: Screening, Hospital Discharge (Day 5) and Study Exit visits.

The following tests will be performed:

- Chemistry: Glucose (random), Blood urea nitrogen, Sodium, Potassium, Chloride, Creatinine, Alkaline Phosphatase, Aspartate Aminotransferase, Alanine Aminotransferase, Total bilirubin, Albumin, Total protein.
- Hematology: Hemoglobin, Hematocrit, White blood cell, Red blood cell, Platelet count, Prothrombin time

Additionally, samples for Serum β -HCG pregnancy test will be collected from women of childbearing potential only at Screening, Day 43-48 visit and Study Exist visit.

Laboratory results for chemistry and hematology as well as changes from baseline will be summarized descriptively by visit. Only subjects with both non-missing baseline and time point values will be summarized at each time point.

Shifts among normal, low and high results (as determined by laboratory normal ranges) from baseline to last available post-baseline assessment will be summarized.

All individual subject clinical laboratory results will be presented in listings by subject and visit. Results of the pregnancy test will be listed.

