##### 10.5.3. Safety Analysis

Safety analysis will be performed on the Safety Population.

The number and percentage of subjects with normal and abnormal findings will be provided for each physical examination in a shift table comparing screening and the end of study evaluation.

Vital signs will be summarized descriptively (mean, standard deviation, median, minimum and maximum). Change from baseline will also be summarized.

Skin photosensitivity is an adverse event of special interest and will be summarized separately from other adverse events at each safety assessment. Changes in skin will be assessed by grade of erythema, edema and blistering. The data will be tabulated by CTCAE grade in the Dermatology/Skin category.

Descriptive statistics for each clinical laboratory test will be presented for the baseline and the end of study assessment. Change from baseline will also be summarized. According to the laboratory normal ranges, laboratory test results will be categorized as low (< lower limit of normal, LLN), normal (within normal range), and high (> ULN). Shift tables, comparing the distributions of these three categories at baseline versus the end of study assessment, will be presented.

---

Concomitant medications will be coded using the WHO Drug dictionary. Medications initiated prior to start of treatment and maintained during the study, or taken during the course of the study will be considered as concomitant medications. Concomitant medications will be summarized according to the preferred terms only.

Adverse events will be coded using the Medical Dictionary for Regulatory Activities (MedDRA). The number and percentage of subjects who experienced any AEs as well as serious AEs will be presented by system organ class (SOC) and by preferred term (PT) within SOC. All AEs will be similarly presented by intensity (mild, moderate, severe or using the CTCAE grading system) and by relationship to treatment (reasonable possibility/no reasonable possibility). One-sided 95% confidence limit will be computed for each AE percentage via exact binomial method (Clopper-Pearson, 1934).

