6. CHANGES IN ANALYSIS FROM PROTOCOL

There are no changes from the protocol-specified analyses.

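### The SAP's only laboratory shift table uses the last available value, so for any subject with a Study Exit sample it cannot count a transient shift seen on Day 5

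*SAP*

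**What the plan says.** SAP 5.4.11.2 schedules chemistry and hematology at "Screening, Hospital Discharge (Day 5) and Study Exit visits". It plans three outputs.

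- Descriptive statistics: "Laboratory results for chemistry and hematology as well as changes from baseline will be summarized descriptively by visit". SAP 5.1 defines these as number of subjects, mean, standard deviation, minimum, median and maximum.
- A shift table of low, normal and high results, "from baseline to last available post-baseline assessment will be summarized".
- A listing of every result by subject and visit.

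No shift table by visit or on the worst value is planned.

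Protocol 10.5.3 describes the shift table differently, as comparing "these three categories at baseline versus the end of study assessment". SAP Section 6 states: "There are no changes from the protocol-specified analyses".

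SAP 4.1 lists laboratory data among the primary safety endpoints. The protocol synopsis names adverse event incidence under the primary endpoint and puts laboratory data under overall safety evaluation.

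**The concern.** The trial asks whether PDT is safe before resection. Of the two routinely scheduled post-baseline laboratory samples, only Day 5 is taken after PDT and before surgery. The Study Exit sample follows PDT, lung resection and roughly three months of later care, so it reflects all three together.

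A rule that takes the last available value selects the exit sample whenever there is one. A subject who is normal at baseline, out of range on Day 5 and normal at exit goes into the normal-to-normal cell. Protocol 1.3 gives a reason to expect such a pattern: it cites studies in which local PDT led to systemic neutrophilia and an acute-phase response. White cell count is in the laboratory panel (Protocol Appendix 13-4).

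There is also a smaller point of consistency. Where a subject has no sample after Day 5, the last available value is the Day 5 value, and it is pooled with values from about Day 105. The protocol's end-of-study comparison does not clearly allow that, and the SAP does not declare the difference.

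**Working it through.** The plan states no figure for the shift table, so there is none to reproduce. The check covers timing, which sample the rule selects, what the other outputs show, and an illustration of size.

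**1. Timing (SAP 2.2.1).** PDT is on Day 3, discharge on Day 5, surgery on Day 13 to 18, and Study Exit on Day 103 to 108 with a window of ±7 days.

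- Day 5 after PDT: 5 − 3 = 2 days.
- Exit window: 103 − 7 = Day 96 to 108 + 7 = Day 115.
- Exit after PDT: 96 − 3 = 93 to 115 − 3 = 112 days.
- Exit after surgery, nominal: 103 − 13 = 90 and 108 − 18 = 90 days.

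**2. Which value enters the shift table.**

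| Subject | Last available value | Day 5 categorised? |
|---|---|---|
| Has a Study Exit sample | Exit, Day 96 to 115 | No |
| Stops early for a reason other than consent withdrawal, and the laboratory tests requested in Protocol 5.3.2.2 are obtained after Day 5 | Discontinuation sample | No |
| Withdraws consent after Day 5, or the discontinuation tests are missed | Day 5, or a discharge-day sample after an extended stay (Protocol 5.2.1.3.2) | Yes, if there is no later sample |

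**3. What else reports Day 5.** The panel has 12 chemistry and 6 hematology tests, 18 in all. With 10 subjects, that is 18 × 10 = 180 Day 5 values, all listed. The by-visit table gives the Day 5 minimum and maximum, so an extreme value is visible. It does not give the number of subjects who moved from normal to low or high. SAP 5.1 limits by-visit summaries to scheduled visits. The documents do not say how repeat tests or discharge-day tests after an extended stay are handled there.

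**4. Illustration of size.** Take n = 10 from SAP 3.1. Two inputs are assumptions that the documents do not supply:

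- p, the chance that a subject has a Day 5 shift that would resolve by exit;
- d, the share of subjects with no laboratory value after Day 5.

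Subjects are taken as independent, and d as unrelated to the shift. The probability that the table shows at least one such shift is:

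- with a Day 5 table: 1 − (1 − p)^10;
- under the current rule: 1 − (1 − p·d)^10.

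| p | Day 5 table | Current rule, d = 0 | d = 10% | d = 20% |
|---|---|---|---|---|
| 0.1 | 0.65 | 0 | 0.10 | 0.18 |
| 0.2 | 0.89 | 0 | 0.18 | 0.34 |
| 0.3 | 0.97 | 0 | 0.26 | 0.46 |

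For example, with p = 0.2 the Day 5 table gives 1 − 0.8^10 = 0.89. The current rule with d = 10% gives 1 − 0.98^10 = 0.18. Even then, the shift is shown as an end-of-study result.

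**The case against.** The strongest reply is that little is lost with about 10 fully listed subjects.

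- The SAP reports more than the protocol asked for. Protocol 10.5.3 planned laboratory descriptive statistics only at baseline and end of study; the SAP's by-visit summary adds Day 5, with minimum and maximum.
- Protocol 8.3 requires the investigator to comment on every out-of-range value. Confirmed worsening to Grade 3 or 4, and any newly found clinically significant value, is recorded as an adverse event. Treatment-emergent events then enter the tables of SAP 5.4.11.1 with exact upper limits.
- The protocol itself specified an end-of-study shift table, and the physical examination shift table also compares Screening with Study Exit.

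All of this stands, and it limits the point to a missing count. It does not remove it. Out-of-range values that are not judged clinically significant can bypass the adverse event route, and a listing is not a summary. The SAP does give normal and abnormal counts by visit for chest X-ray, including the discharge visit (5.4.12), but none for laboratory results.

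A reader might infer three stronger things that the documents do not support.

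- That Day 5 is never categorised. It can be, for a subject with no later sample.
- That the table shows recovery and not PDT toxicity. A persistent effect would still appear at exit.
- That laboratory tests are drawn at only three times. The protocol also provides for discharge-day tests after an extended stay, for discontinuation tests and for repeat testing.

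**Conclusion.** The point holds in a limited form. For every subject with a Study Exit sample, the only laboratory shift table omits the one routinely scheduled sample between PDT and surgery, so it cannot count transient post-PDT shifts. The gap is one of categorical tabulation, mainly for values that do not become adverse events. No data are lost and no inference in the plan depends on this table.

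The probabilities in the illustration rest wholly on assumed values of p and d. The conclusion about which sample is selected does not.

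The difference between the SAP's last available value and the protocol's end-of-study value is undeclared but small. The two coincide for subjects with an exit sample. They can differ mainly after consent withdrawal, when Protocol 5.3.2.1 stops further data collection. The documents give no dropout rate, so the number of subjects affected is unknown.

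Priority is low: a nearly free improvement.

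**What to change.** In SAP 5.4.11.2:

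1. Keep an end-of-study shift table as in Protocol 10.5.3. Say which value counts as end of study for a subject without an exit sample, so that Day 5 values are not pooled with it unmarked.
2. Add a baseline-to-Day 5 shift table, a baseline-to-worst post-baseline shift table, or both. The worst-value table should include unscheduled and repeat tests and discharge-day tests after an extended stay. For tests where both directions matter, tabulate worst low and worst high separately.
3. Record the change in SAP Section 6.

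The cost is one or two extra tables from data already collected, with no new samples and no burden on subjects.
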